3 SYNOPSIS

Investigation title	Randomized controlled trial of immediate versus delayed cochlear implantation.
Short Study Title	Hearing Loss in Older Adults Study ¹
Investigation number	CLTD5693
Total expected duration of the clinical investigation	30 months
Expected duration per subject	15-21 months
Investigational design	Prospective, 1:1 randomized controlled trial of immediate versus delayed cochlear implantation (CI) on hearing handicap, communicative function, loneliness, mental wellbeing, and cognitive functioning. Subjects are randomized 1:1 to an immediate cochlear implant intervention arm versus a hearing aid control intervention.
Number of subjects	Up to 60 subjects in a 1:1 allocation
Inclusion criteria	
 1. Aged 65 to 85 years, inclusive 2. Community-dwelling 3. Proficient in English 4. Oral communicator 5. PTA (500, 1000 & 2000 Hz) \geq 70 dB HL hearing loss duration \geq1 and no more than 30 years. 6. Active hearing aid users: daily use of hearing aids. 7. Hearing Handicap Inventory for the Elderly - Screening (HHIE-S): Score \geq 24 indicating a significant hearing handicap. 8. Hearing Impaired Montreal Cognitive Assessment (HI-MoCA): Score \geq 20 indicating mild cognitive impairment to normal cognitive function. 9. Cochlear implant candidacy: Participants must have postlinguistic onset sensorineural hearing loss and meet applicable FDA and/or Medicare candidacy criteria for cochlear implantation. 10. Willingness to consent for the study, to be randomized to either the immediate or delayed cochlear implantation arm, to utilize bimodal hearing for the duration of the trial (if clinically appropriate) and follow the study protocol for the duration of the trial.
Exclusion criteria	
 1. Prelingual or perilingual severe-to-profound hearing loss. 2. Previous cochlear implantation in either ear. 3. Hearing loss of neural or central origin. 4. Permanent conductive hearing impairment (e.g. otosclerosis). 5. Medical, audiological or psychological conditions, as judged by the investigator that might contraindicate participation in the clinical investigation. 6. Self-reported disability in \geq 2 activities of daily living. 7. Unwilling to wear a device or comply with the surgical and rehabilitation requirements of the study. 8. Vision impairment: worse than 20/40 (corrected) on a Near Vision Card.

¹ As registered on ClinicalTrials.gov

Primary objective	To determine the effect of treating hearing loss with cochlear implantation (CI) versus continued use of hearing aids (HA) on hearing satisfaction using the Speech, Spatial and Qualities of Hearing (SSQ12) in older adults.
Primary endpoint	Assessment of the impact of cochlear implantation versus continued hearing aid use on hearing satisfaction as measured using the Speech, Spatial and Qualities of Hearing (SSQ12) at Follow-up Visit 1 (FUV1).
Secondary objective	To assess cognition in older adults with hearing loss with a Cogstate® battery of neuropsychological tests.
Secondary endpoint	Assessment of the impact of cochlear implantation versus continued hearing aid use on cognition with a Cogstate® battery of neuropsychological tests at Follow-up Visit 1 (FUV1).
Ancillary analyses	
Ancillary analyses include:
 
 Investigating treatment effect on neuropsychological measures using the Hearing Impaired Montreal Cognitive Assessment (HI-MoCA) at Follow-Up Visit 1 (FUV1). Investigate the treatment effect of immediate cochlear implantation vs continued use of HAs on psychosocial measures such as loneliness and depression using the UCLA Loneliness Scale and the Geriatric Depression Scale (GDS) at Follow-up Visit 1 (FUV1). Investigate the treatment effect of immediate cochlear implantation vs continued use of HAs on physical functioning measures such as daily activity and lifestyle using the Lifestyle Activity Questionnaire (LAQ) at Follow-up Visit 1 (FUV1). To determine the effect of treating hearing loss with CI versus continued use of HAs on quality of life in each arm (immediate CI vs continued HA use) using the Health Utilities Index Mark III (HUI-III) at Follow-up Visit 1 (FUV1). To quantify pre- to post-implantation outcomes associated with cochlear implantation. 
 Self-reported hearing ability using the Hearing Handicap Inventory for the Elderly – Screening (HHIE-S). Outcomes for both the treated ear and everyday listening condition (bimodal): speech perception in quiet using CNC Words presented 60 dBA and speech perception in speech-weighted noise using AzBio sentences presented at 65 dBA using a +10 dB Signal to Noise Ratio (SNR). Investigate maintenance of treatment effect on neuropsychological, psychosocial, physical, quality of life and audiometric measures obtained at: 
 FUV2 compared to FUV1 (Arm A). FUV3 compared to FUV2 (Arm B).

4 INVESTIGATION DESIGN

5 INVESTIGATION PROCEDURES

Procedure	Screening POV1 Arm A&B	Baseline POV2 Arm A&B	Surgery Arm A	Clinical Review Visits Arm A&B	FUV1 Arm A&B	Surgery Arm B	FUV2 Arm A&B	FUV3 Arm B
Timeline		4-6 weeks from POV1 (+/- 2 weeks)	1 week from POV2 (+/- 1 week)	1-5 months from POV2 (+/- 2 weeks)	6 months from POV2 (+/- 2 weeks)	1 week from FUV1 (+/- 1 week)	12 months from POV2 (+/- 4 weeks)	18 months from POV2 (+/- 4 weeks)
Consent	X							
Demographics	X							
Concomitant Medications		X	X	X	X	X	X	X
Adverse Events		X	X	X	X	X	X	X
Medical History		X						
Hearing History	X							
Randomization	X							
HI-MoCA	X				X			
Near Vision Screening	X							
Activities of daily living	X				X		X	X
HHIE-S	X				X		X	X
Cogstate computerized test battery	X	X			X		X	X
Imaging				X-ray (Arm A)	CT scan ² (Arm A)		X-ray (Arm B)	CT scan ³ (Arm B)

² CT scan will occur post-surgery and prior to FUV1 (Arm A)

³ CT scan will occur post-surgery and prior to FUV2 (Arm B)

Procedure	Screening POV1 Arm A&B	Baseline POV2 Arm A&B	Surgery Arm A	Clinical Review Visits Arm A&B	FUV1 Arm A&B	Surgery Arm B	FUV2 Arm A&B	FUV3 Arm B
Timeline								
SSQ12		X			X		X	X
UCLA Loneliness Scale		X			X		X	X
GDS-short form		X			X		X	X
LAQ		X			X		X	X
HUI-III		X			X		X	X
Rehabilitation				X (4-6 visits)				
Unaided air conduction testing	X				X		X	X
Aided soundfield testing		X		X (3 mths)				
Tympanometry	X				X		X	X
Aided AzBio Sentences in Noise								
Ear to be implanted/implant ear		X			X		X	X
Everyday Listening		X			X		X	X
Aided CNC Words in Quiet								
Ear to be implanted/implant ear		X		X (3 mths)	X		X	X
Everyday Listening		X			X		X	X
Datalogs		X		X	X		X	X

6 BACKGROUND AND RATIONALE

Prospective studies have demonstrated reduced hearing handicap following cochlear implantation in adults (1, 2). However this has not been assessed in a randomized clinical trial. Epidemiologic data strongly suggest that age-related peripheral hearing loss is independently associated with accelerated rates of cognitive decline and incident dementia (2, 3). A conceptual model (Figure 1) developed by Lin and Albert (3) depicts the causal mechanisms that may mediate the effects of hearing impairment on impaired cognitive functioning and dementia. Common factors that could underlie a simple correlation between hearing and cognition include age, shared pathologic etiologies (e.g., diabetes, hypertension, neurodegenerative processes), and demographic factors (e.g., education). In contrast, mechanistic pathways through which hearing loss could contribute to poorer cognitive functioning include effects on cognitive load, brain structure/function, and decreased social engagement. The effects of poor audition and distorted peripheral encoding of sound on cognitive load could reduce capacity for other functions, such as cognition. Changes in brain structure could lead to downstream changes in brain function which may affect cognitive processing (4-10). Alternatively reduced social engagement could be a mediating factor.

[figure not shown]

Figure 1. Conceptual model of the association of hearing impairment with cognitive functioning and dementia.

6.1 Hearing interventions to reduce cognitive decline

Whether existing interventions for hearing loss can mitigate declines in cognitive function is unknown. Previous studies provide proof-of-principle that interventions that provide enhanced auditory stimuli can engage and modify the hypothesized mechanistic pathways linking hearing and cognition through reducing cognitive load (11-14), altering functional pathways and brain structure (4-10), and improving social engagement. A planned trial, the Aging, Cognition, and Hearing Evaluation Trial (ACHIEVE), will investigate the impact of best practice hearing health care, including the provision of hearing aids, on cognitive functioning in older adults with *mild-to-moderate* hearing loss.

The trial described in this protocol will be the first randomized controlled trial to investigate the impact of cochlear implantation versus continued use of hearing aids on cognitive function in individuals with severe-to-profound hearing loss. To date, only one published study has examined the effects of cochlear implantation on cognition in older adults (15). This longitudinal, multi-center study examined 94 adults aged 65-85 years who met candidacy requirements for a cochlear implant.

Neuropsychological tests, speech perception tests and quality of life and depression questionnaires were administered before cochlear implantation (baseline) and at 6 and 12 months post cochlear implant activation.

To avoid potential confounding effects of audibility and diminished speech perception understanding, all instructions for the neuropsychological tests were provided in written form in the Mosnier et al. study. The number of individuals with scores classified as abnormal decreased after implantation: At baseline, 25% of subjects had normal scores on six cognitive tasks, 31% had one abnormal score, 24% had two abnormal scores, and 20% had three abnormal scores. At 12 months, 40% had normal scores on six cognitive tasks, 33% had one abnormal score, 22% had two abnormal scores and only 5% had three abnormal scores. While informative, the Mosnier et al. study did not have a control arm, so it is possible that some of the improvement could be attributed to learning effects. The CI-Cognition trial described in this protocol incorporates a watchful waiting control arm and overcomes this limitation.

An additional study, the Studying Multiple Outcomes after Aural Rehabilitative Treatment (SMART) study prospectively assessed cognitive functioning in 145 adults aged 50 years or older before receiving hearing aids or cochlear implants and at 6 and 12 months after treatment (16). Data from Li et al showed improved cognitive performance at 6 and 12 months, albeit with a smaller effect size than that found in the study previously reviewed by Mosnier et al (15). Li et al. also reported that CI subjects had significantly greater loneliness, social isolation and poorer hearing and communicative function compared to HA subjects.

7 JUSTIFICATION FOR THE DESIGN OF THE CLINICAL INVESTIGATION

We propose a randomized controlled trial design whereby up to sixty (60) participants with severe-to-profound hearing loss are randomized 1:1 to an immediate cochlear implant (CI) intervention (Arm A) versus a hearing aid (HA) control intervention (Arm B). The immediate CI treatment arm will be implanted with either the Cochlear Nucleus® Profile™ Slim Modiolar (532) cochlear implant or the Cochlear Nucleus® Profile™ Plus CI632 cochlear implant with Slim Modiolar electrode. The HA control intervention provides a comparison arm representing standard clinical care for conventional amplification (HAs). Randomization seeks balance between the two arms. The control arm will also receive the CI intervention (Nucleus CI532 or CI632 implant) after a watchful waiting delay period of 6 months post baseline. Both arms will receive the neuropsychological battery twice before the intervention (once at screening and again at baseline) to minimize the impact of learning effects on analyses of post-intervention cognitive change.

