9.2 Assessments

9.2.1 Neuropsychological Test Battery

9.2.1.1 Hearing Impaired Montreal Cognitive Assessment (HI-MoCA)

The Montreal Cognitive Assessment (MoCA) is an interviewer administered screening tool used to detect mild cognitive impairment (18). It has been demonstrated to have high sensitivity and specificity for detecting mild cognitive impairment (18-20). The MoCA has been used in clinical evaluations to assess cognitive function and treatment effect in older patients undergoing cochlear implantation (21, 22). The MoCA has been converted into a timed PowerPoint (Microsoft Corp., Redmond, WA) presentation, and verbal instructions converted into visual instructions to assist in the assessment of severely hearing impaired adults - the Hearing Impaired Montreal Cognitive Assessment (HI-MoCA) (23). The HI-MoCA has been validated as a screening for cognitive impairment in the severely hearing impaired older populations. No conversion factor from HI-MoCA to MoCA scores were required in the cohort of cognitively intact subjects. The HI-MoCA will be used in the clinical investigation to assess cognitive function of older adults undergoing cochlear implantation.

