9.3.5 Preoperative Visit 2 (POV2) - Baseline

Preoperative visit 2 (POV2) baseline will occur 4-6 weeks post POV1 (+/- 2 weeks) to enable scheduling of surgery for Arm A subjects. Both Arm A and Arm B subjects will complete POV2 with appropriately fit hearing aids and glasses (if required). The full neuropsychological battery in addition to the audiology, psychosocial, physical, and quality of life metrics will be completed as described in Section 9.2. Speech recognition will be assessed in the everyday listening condition (aided bilaterally) and the ear to be implanted listening conditions with the contralateral ear plugged. Datalogs will be retrieved for the hearing aid.

Medical history will be completed minimally via the ACE 27 index. The Investigator or appropriately delegated staff may add additional otologic history (hearing history) which they deem relevant to the study.

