6.1.2 Visit Windows

Unless otherwise specified, visit assessments will be analyzed for each analysis time point as described in Sections 6.6 and 6.7.

Each test measure by arm/visit abbreviation is described in the table below.

Where:

A = Arm A, B = Arm B, and x = number of months post-baseline measure.

[figure not shown]
Procedure	Screening POV1	Baseline POV2	FUV1	FUV2	FUV3
HI-MoCA	A0 or B0		A6 or B6	A12 or B12	B18
HHIE-S	A0 or B0		A6 or B6	A12 or B12	B18
Cogstate		A0 or B0	A6 or B6	A12 or B12	B18
SSQ12		A0 or B0	A6 or B6	A12 or B12	B18
UCLA		A0 or B0	A6 or B6	A12 or B12	B18
GDS		A0 or B0	A6 or B6	A12 or B12	B18
LAQ		A0 or B0	A6 or B6	A12 or B12	B18
HUI-III		A0 or B0	A6 or B6	A12 or B12	B18
CNC words		A0 or B0	A6 or B6	A12 or B12	B18
AzBio sentences		A0 or B0	A6 or B6	A12 or B12	B18
Audiometric thresholds	A0 or B0		A6 or B6	A12 or B12	B18

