6.7.1.2 Tertiary Analyses

All tertiary analyses will be presented using descriptive statistics and analyzed using a t-test to compare the mean score of the cochlear implant Arm A to that of the hearing aid control Arm B at various time points. As these tertiary analyses are exploratory in nature, there will be no adjustment for multiple comparisons, no formal hypotheses testing and no statement of statistical significance.

Investigating treatment effect on:

- Neuropsychological outcomes:
 - Cogstate¹:
 - ☒ Detection Test – speed of performance
 - ☒ Groton Maze Learning Test – number of errors
 - ☒ Identification Test – speed of performance
 - ☒ One Card Learning Test – accuracy of performance
 - ☒ One Back Test – speed of performance
 - A6 vs B6 (treatment effect)
 - A0 vs B0 (population)
 - A6 vs B12 (6 months post-CI)
 - A12 vs B18 (12 months post-CI)
 - A0 vs A6 vs A12 (longitudinal treatment effect)
 - B6 vs B12 vs B18 (longitudinal treatment effect)
 - HI-MoCA:
 - ☒ A6 vs B6 (treatment effect)
 - ☒ A0 vs B0 (population)
 - ☒ A6 vs B12 (6 months post-CI)

¹ A sensitivity analyses will be conducted with test data integrity failures excluded if the integrity failure rate is greater than 10%.

Statistical Analysis Plan		Page 13 of 16
Sponsor	Study	CIP Version
Cochlear	Hearing Loss in Older Adults	9.0

- ☒ A12 vs B18 (12 months post-CI)
- ☒ A0 vs A6 vs A12 (longitudinal treatment effect)
- ☒ B6 vs B12 vs B18 (longitudinal treatment effect)
- Psychosocial measures:
 - UCLA Loneliness Scale:
 - ☒ A0 vs B0 (population)
 - ☒ A6 vs B12 (6 months post-CI)
 - ☒ A12 vs B18 (12 months post-CI)
 - ☒ A0 vs A6 vs A12 (longitudinal treatment effect)
 - ☒ B6 vs B12 vs B18 (longitudinal treatment effect)
 - Geriatric Depression Scale (GDS):
 - ☒ A0 vs B0 (population)
 - ☒ A6 vs B12 (6 months post-CI)
 - ☒ A12 vs B18 (12 months post-CI)
 - ☒ A0 vs A6 vs A12 (longitudinal treatment effect)
 - ☒ B6 vs B12 vs B18 (longitudinal treatment effect)
- Audiometric measures:
 - HHIE-S:
 - ☒ A0 vs B0 (population)
 - ☒ A6 vs B12 (6 months post-CI)
 - ☒ A12 vs B18 (12 months post-CI)
 - ☒ A0 vs A6 vs A12 (longitudinal treatment effect)
 - ☒ B6 vs B12 vs B18 (longitudinal treatment effect)
 - SSQ12:
 - ☒ A0 vs B0 (population)
 - ☒ A6 vs B12 (6 months post-CI)
 - ☒ A12 vs B18 (12 months post-CI)
 - ☒ A0 vs A6 vs A12 (longitudinal treatment effect)
 - ☒ B6 vs B12 vs B18 (longitudinal treatment effect)

Statistical Analysis Plan		Page 14 of 16

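### HI-MoCA lacks the second pre-implant session that Section 7 relies on to limit learning, so Arm A's A0-to-A6 change may include first-retest practice

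*Protocol*

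**What the plan says.** Protocol Section 7 commits to this: "Both arms will receive the neuropsychological battery twice before the intervention (once at screening and again at baseline". The stated reason is "to minimize the impact of learning effects on analyses of post-intervention cognitive change".

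Protocol Section 9.2.1 lists two instruments under the neuropsychological battery. The first is "9.2.1.1 Hearing Impaired Montreal Cognitive Assessment (HI-MoCA") and the second, at 9.2.1.2, is Cogstate. Section 9.3.4 refers to 9.2.1 for the POV1 testing. Section 9.3.5 says of POV2: "The full neuropsychological battery in addition to the audiology, psychosocial, physical, and quality of life metrics will be completed as described in Section 9.2".

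The procedures table (Protocol Section 5) differs. Its Cogstate row begins "Cogstate computerized test battery X X", with marks at POV1 and POV2, and continues at FUV1, FUV2 and FUV3. Its HI-MoCA row has two marks only, at POV1 and FUV1.

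SAP 6.1.2 sets the time-point labels, in which "A = Arm A, B = Arm B, and x = number of months post-baseline measure". The HI-MoCA row reads "HI-MoCA A0 or B0 A6 or B6 A12 or B12 B18"; its first entry is under POV1 and its POV2 cell is empty. For Cogstate, A0/B0 is under POV2.

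SAP 6.7.1.2 then lists, for HI-MoCA, "A0 vs A6 vs A12 (longitudinal treatment effect") in Arm A and the B6, B12, B18 series under the same label in Arm B. It also lists A6 vs B6, A6 vs B12 and A12 vs B18. All are tertiary and exploratory, without formal testing or any claim of significance.

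**The concern.** The double pre-intervention session lets the first sitting absorb familiarisation, so that change is measured from the second. The schedule does this for Cogstate: POV1 is the practice session and POV2 the baseline. For HI-MoCA, the table and the SAP both use the first sitting in the study as the baseline. Any improvement that comes only from having seen the test once before then falls inside Arm A's A0-to-A6 change, and the SAP's label attributes that change to treatment.

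Protocol Section 6.1 faults an earlier uncontrolled implant study because learning might explain part of its improvement. A within-arm HI-MoCA change measured from first exposure has the same weakness.

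There is also a conduct problem. Section 9.3.5 and the procedures table give sites opposite instructions about HI-MoCA at POV2. How many earlier sittings lie behind an A6 score therefore depends on which one a site follows.

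**Working it through.** The plan states no figure on this point, so the check is a count of sittings.

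**Inputs.** Visits with HI-MoCA come from the procedures table (Protocol Section 5), the visit text (Sections 9.3.4, 9.3.5, 9.3.9, 9.3.13 and 9.3.14) and the visit table in SAP 6.1.2. The contrasts come from SAP 6.7.1.2.

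**Step 1: sitting number at each visit.**

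| Source followed | POV1 | POV2 | FUV1 | FUV2 | FUV3 (Arm B) |
|---|---|---|---|---|---|
| HI-MoCA, procedures table | 1 | none | 2 | none | none |
| HI-MoCA, SAP 6.1.2 | 1 | none | 2 | 3 | 4 |
| HI-MoCA, protocol visit text | 1 | 2 | 3 | 4 | 5 |
| Cogstate, table and SAP | 1 | 2 | 3 | 4 | 5 |

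For Cogstate, the SAP labels start at POV2; the POV1 sitting comes from the procedures table.

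**Step 2: sittings spanned by Arm A's A0-to-A6 change.**

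- HI-MoCA as scheduled (table and SAP): 1 to 2.
- HI-MoCA if sites follow 9.3.5 and the SAP keeps A0 at POV1: 1 to 3.
- HI-MoCA if given at POV2 and baselined there: 2 to 3.
- Cogstate as planned: 2 to 3.

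Only the first two include the step from first to second sitting, which the double session was meant to keep out.

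**Step 3: between-arm HI-MoCA contrasts on the SAP schedule.**

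- A6 vs B6: sitting 2 vs 2, balanced.
- A6 vs B12: sitting 2 vs 3.
- A12 vs B18: sitting 3 vs 4.

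In the last two, Arm B has one more earlier sitting.

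**Step 4: how much practice could sit in A0-to-A6.** The documents give no practice figure for HI-MoCA, so this is illustration only. Let g be the gain from sitting 1 to 2, and let each later gain be r times the one before, with r assumed to be 0.25 to 0.5. Practice in A0-to-A6 is then:

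- as scheduled: g
- 9.3.5 followed, POV1 baseline kept: g + g×r = g(1 + r)
- POV2 sitting used as baseline: g×r

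| g (assumed, points) | As scheduled | 9.3.5 with POV1 baseline | POV2 baseline |
|---|---|---|---|
| 0 | 0 | 0 | 0 |
| 0.5 | 0.5 | 0.625 to 0.75 | 0.125 to 0.25 |
| 1 | 1.0 | 1.25 to 1.5 | 0.25 to 0.5 |
| 2 | 2.0 | 2.5 to 3.0 | 0.5 to 1.0 |

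Whatever the value of g, a POV2 baseline removes the first-retest step but not all practice.

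**Step 5: FUV2 and FUV3.** SAP 6.1.2 uses HI-MoCA scores at A12, B12 and B18, and Sections 9.3.13 and 9.3.14 ask for the full battery. The procedures table marks no HI-MoCA at either visit. On the table alone, the A12 value and every post-implant HI-MoCA value in Arm B would be missing.

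**The case against.** **The battery may mean Cogstate alone.** The secondary objective and endpoint use similar words for Cogstate only, and Cogstate is given at both POV1 and POV2. On that reading Section 7 is true as it stands. Part of this survives: the term is used loosely. But 9.2.1 puts HI-MoCA first under the battery heading, and 9.3.4 and 9.3.5 refer the reader to that description. Even on the narrow reading, the SAP still labels a change from first exposure as a treatment effect.

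**It is a contradiction, not a settled absence.** Section 9.3.5 does call for the full battery at POV2, so HI-MoCA may be given there. This is fair, and the point is worded accordingly. It does not rescue the analysis: with the SAP baseline left at POV1, the change then spans three sittings instead of two.

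**The size is unknown.** This stands. The retest is about six months later, the practice gain could be zero, and *first session* means first in the study, since earlier clinical testing is not recorded.

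**Stronger readings a reader might infer.** One is that practice would inflate Arm A's gain relative to Arm B's and so look like a benefit of earlier implantation. The documents do not support that. SAP 6.7.1.2 plans no comparison of gains between arms, and in the planned A6 vs B12 and A12 vs B18 contrasts exposure favours the delayed arm. The arms' series do start one sitting apart, but that comes from the delayed-start design. It applies equally to Cogstate (A0 is sitting 2, B6 is sitting 3), and moving the HI-MoCA baseline would not remove it.

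Another is that the randomised HI-MoCA comparison is biased. A6 vs B6 is a t-test of means with no baseline term, and exposure is equal provided both arms at a site follow the same schedule.

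**Conclusion.** The inconsistency is real and lies in current text. Two tables in two documents leave HI-MoCA out of POV2, while Sections 7 and 9.3.5, read with 9.2.1, put it there. As scheduled, Arm A's HI-MoCA A0-to-A6 change runs from sitting 1 to sitting 2 and may include first-retest practice. It cannot be read as treatment effect alone.

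The session counts rest on the documents. The points in the illustration rest on assumed g and r and show only how practice would enter.

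The consequence is limited. The randomised A6 vs B6 comparison is balanced for exposure. The primary SSQ12 endpoint and the secondary Cogstate endpoint at FUV1 are unaffected. The HI-MoCA analyses are tertiary, with no formal testing. This is worth correcting but does not threaten the trial's main conclusions.

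**What to change.** Reconcile Protocol Section 7, Section 9.3.5, the procedures table and SAP 6.1.2 on HI-MoCA at POV2, in one of two ways.

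1. Mark HI-MoCA at POV2 for both arms in the procedures table, and set its A0/B0 to POV2 in SAP 6.1.2, as for Cogstate. Keep the POV1 score for eligibility. The cost is a few minutes of subject time at a visit where 9.3.5 already asks for the full battery.
2. Leave HI-MoCA out of POV2. Limit the learning statement in Section 7 to Cogstate, bring 9.3.5 into line, and present HI-MoCA A0 vs A6 vs A12 in SAP 6.7.1.2 as pre-to-post change that includes practice, not as a treatment effect. This needs wording changes only and no extra testing.

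Under either option, settle HI-MoCA at FUV2 and FUV3 in the same edit. The procedures table omits it there, while SAP 6.1.2 and 6.7.1.2 depend on A12, B12 and B18.
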